## 9.0 Setting

**Directions: Describe the sites and locations where your research team will conduct the research.**

Baseline assessment meeting: Participants will meet the Nourish research team at a reserved room located at a branch of the Cleveland Public Library. Weekly Nourish classes: For the duration of 8 weeks, the Nourish culinary education intervention will take place at a community teaching kitchen located at Dave's Market Midtown ([name]) or CornUcopia ([name]). Second-assessment meeting: Participants will meet the Nourish research team at a reserved room located at a branch of the Cleveland Public Library. Focus Group Series: Participants who complete at least 7 of the 8 Nourish classes will be invited to participate in 2, 90-minute semi-structured focus groups. These will take place online via Zoom.

## 10.0 Consent Process

**Indicate whether you will be obtaining consent:**

Yes       No

**If yes, answer the following questions:**

1. Describe *who* will consent the subjects and *where* the consent process will take place: The study coordinator and principal investigator will obtain informed consent. Informed consent will be obtained from registered participants prior to their participation in the first Nourish class session. The consent process will take place at a reserved room located at a branch of the Cleveland Public Library 2 weeks before the first Nourish class session. Participants who are eligible for the focus groups, will be consented during the post intervention assessment meeting in a reserved room located at a branch of the Cleveland Public Library. For the 2, 90 minutes semi-structured focus groups, we will attach a consent form to the recruitment letters provided to eligible participants (those completing at least 7 Nourish classes).
2. The time that will be devoted to the consent discussion: A minimum of 20 minutes will be devoted to the consent discussion for each participant. The explanation of the research and participation explanation will summarize the objectives of the research; overview of the Nourish curriculum; potential risks of participation; expectations of participation, including participation in weekly nutrition/cooking classes, weekly surveys, and outside-of-class discussions. For the focus group consenting process, we will begin the focus group with an overview of the consent form that has been previously provided to them and provide an opportunity for questions. This is expected to take about 5 minutes.
3. Any waiting period available between informing the prospective subject and obtaining the consent: If requested, a participant will be granted a waiting period after providing an explanation of the research and participation. It is anticipated that the Nourish team will receive consent from participants while in person after the consent discussion and before completing baseline assessments.

4. Steps that will be taken to ensure the research participants' understanding: During the consent conversation, the research team will periodically ask potential research participants if they understand the information being shared with them, and whether or not they have any questions.
5. Any process to ensure ongoing consent: Ongoing consent will be implied by the completion of weekly class evaluation surveys.
6. Steps that will be taken to minimize the possibility of coercion or undue influence to the subjects: Potential participants will be given ample time to review all consent documents. The research team will answer all questions, and offer a waiting period between informing the potential participant and obtaining consent if requested.

### For Adult Participants

**Indicate if you will be asking for a waiver or alteration of consent process or documentation (consent will not be obtained, or written consent will not be documented)**

Yes       No

**If yes**, explain how the research involves no more than minimal risk. Note: We are only asking for a waiver of signed consent for the focus groups. The focus groups will be conducted online and will not ask personal questions. It will only consist of feedback questions about the Nourish classes and evaluation procedures.

**Indicate which part of the consent process you are requesting to be waived or altered and the questions following your choice(s):**

I will obtain consent, but not participant's signature. (Waiver of documentation)

1. Give the rationale for the request of a waiver of signed consent. We seek a waiver of signed consent for the focus groups because they will be completed online, and it would be a participant burden to collect signatures from participants.
2. Please describe how you will be documenting that a participant has consented. If a participant chooses to participate in the focus group, this will be implied consent.
3. Indicate if the subjects will be provided with written information about the study, and provide justification if you will not be providing a written explanation of the research. We will provide a printed copy of the consent form with the recruitment letter.

- I will obtain consent, but request a waiver of some of the elements of consent (e.g. use of deception). (Alteration)
- I will not obtain any consent; I am requesting a full waiver of consent.

**Only answer if you are requesting an alteration of consent, or a full waiver of consent, please answer the following:**

1. Give the rationale for the request of a waiver or alteration of the consent process. [Click here to enter text.](#)
2. Explain why the waiver or alteration of consent will not adversely affect the rights and welfare of the participants. [Click here to enter text.](#)
3. Explain why the research could not practicably be carried out without the waiver or alteration of consent. [Click here to enter text.](#)
4. Indicate if the subjects will be provided with additional information about the study after participation. [Click here to enter text.](#)

*\*Be sure to upload a consent script or information sheet with your study protocol*

#### **Additional Considerations for Consent Process with Adults**

##### Non English Speakers (Please select one)

- I am not enrolling non-English speaking individuals in this research study. The following is justification for why non-English speaking individuals cannot be enrolled: Non-English speaking individuals will be excluded because we will be cooking in small groups during the intervention. While the risk of injury is no greater than that in everyday life activities, it is important that all participants be able to communicate with each other to maintain a safe cooking environment.
- I will be targeting non-English speaking adults
  1. Describe the process to ensure that the oral and written information provided to those research participants will be in that language during initial consent as well as throughout the study. [Click here to enter text.](#)
  2. List the language(s) other than English that will be targeted: [Click here to enter text.](#)
- I am not targeting non-English speaking individuals. If a non-English speaking individual is eligible for the study, we will use the following procedures to enroll:
  1. Describe the process to ensure that the oral and written information provided to those research participants will be in that language during initial consent as well as throughout the study. [Click here to enter text.](#)

**Adults Unable to Consent**

I am not enrolling adults unable to consent in this research study – *please leave the rest of this section blank.*

There is an anticipated direct benefit to the subject. Explain: [Click here to enter text.](#)

There is NOT an anticipated direct benefit to the subject. Explain: Click here to enter text.

1. Describe the process to determine whether an individual is capable of consent. [Click here to enter text.](#)
2. List the individuals from whom permission will be obtained in order of priority (e.g. durable power of attorney for health care, court appointed guardian for health care decisions, spouse, and adult child). [Click here to enter text.](#)
3. For research conducted outside of the state, provide information that describes which individuals are authorized under applicable law to consent on behalf of a prospective subject to their participation in the procedure(s) involved in the research. [Click here to enter text.](#)
4. Describe the process for assent of the research participants. Indicate:
  - Which subjects that are unable to consent will be required to give assent? If not all, explain why. [Click here to enter text.](#)
  - Describe whether assent of the research participants will be documented and the process to document assent. [Click here to enter text.](#)

The subject will be informed about the research to the extent compatible with the subject's understanding.

Subjects will be closely monitored.

The subject will be withdrawn if they appear unduly distressed.

**Research Participants Who Are Not Yet Adults (infants, children, teenagers)**

I am not enrolling participants who are not yet adults in this research study. – *please leave the rest of this section blank*

1. Will parental permission be obtained from:
  - One parent even if the other parent is alive, known, competent, reasonably available, and shares legal responsibility for the care and custody of the child

- Both parents unless one parent is deceased, unknown, incompetent, or not reasonably available, or when only one parent has legal responsibility for the care and custody of the child
- Requesting a waiver of parental permission

**If you are getting parental/guardian permission:**

a. Indicate how you will be documenting the permission:

- Signed consent form
- Requesting a waiver of documentation of parental permission

b. Describe whether permission will be obtained from individuals other than parents, and if so, who will be allowed to provide permission. Describe the process used to determine these individuals' authority to consent to each child's participation in research. [Click here to enter text.](#)

**If a waiver of parental permission is being requested:**

a. Describe how the study is designed for a subject population for which parental/guardian permission is not a reasonable requirement to protect the subjects, if applicable. [Click here to enter text.](#)

b. Describe how the research could not practicably be carried out without the waiver of parental permission. [Click here to enter text.](#)

c. Indicate if the subjects will be provided with additional information about the study after participation. [Click here to enter text.](#)

2. Will assent be obtained from:

- all of the children
- some of the children
- none of the children

If assent will be obtained from some children, indicate which children will be required to assent. [Click here to enter text.](#)

If assent will be obtained from none of the children, indicate the rationale. [Click here to enter text.](#)

When assent of children is obtained, describe how it will be documented. [Click here to enter text.](#)

3. For children who are pregnant, describe how assent and permission are obtained. [Click here to enter text.](#)

N/A

## 11.0 Sharing of Results with Research Participants

Individual test or research results will be shared with research participants (this is not referring to sharing through standard academic channels, e.g., publishing, presentation, etc.):

Yes  No

If yes, describe how the results will be shared. [Click here to enter text.](#)

Individual test results will be shared with others (e.g., lab results given to a primary care physician):

Yes  No

If yes, describe with whom and how the results will be shared. Click here to enter text.

## 12.0 Study Design/Procedures

### Directions:

- 1) **Describe the overall study design (e.g.: single visit, single-blind, double-blind, non-randomized, randomized, blood draw, investigational drug, device etc.).**
- 2) **Provide a description of all study-related research procedures being performed, including the length of time involved.**
- 3) **Include procedures being performed to monitor research participants for safety or minimize risks.**
- 4) **Describe the source records including medical or educational records, which will be used to collect data about subjects.**
- 5) **Include a description of any device being used to collect data (e.g., eye tracker, step counter). If the device itself is being studied, include additional information in Section 29.**

1. The study follows a randomized controlled trial with a delayed intervention control design. The immediate cooking class group will receive their intervention in week 3 of the study, and the delayed cooking class group will receive their intervention in week 13 of the study.

2. *Baseline assessment meeting:* Regardless of randomized group, all participants will attend this meeting in week 1. Participants will come to a branch of the Cleveland Public Library to sign their consent form and complete the survey portion of their baseline assessment, consisting of Percieved Stress Scale, USDA Food Security Screener, and the Food Literacy, Environment, and Waste (FLEW) assessment which will be conducted via Qualtrics on tablets provided by the researchers. Two aspects of the baseline evaluation will be conducted after the baseline meeting: a) a series of two 24-hour dietary recalls (via phone calls) lasting approximately 30 minutes each and b) participants will be asked to weigh and log their food waste for one week. During the baseline assessment meeting, participants will be asked to share their phone number and participants will be given a kitchen food scale and waste log. They will be asked to return the log on the first day of class. Additionally, participants will be told what they can expect to happen at each Nourish class and will be coached on how to sign up for GroupMe to receive out-of-class information about Nourish. The duration of the baseline assessment meeting will be

approximately 60 minutes, and will occur two weeks before the immediate cooking classes group's 8-week Nourish class sessions begin.

*Weekly Nourish classes:* Each Nourish class will last 90 minutes, and will run for 8 consecutive weeks, with one class per week. The immediate cooking class group will receive the Nourish classes in weeks 3-10, and the delayed intervention group will commence the Nourish intervention in weeks 13-20 (after the second intervention assessment period is complete).

Nourish will be held in the teaching kitchen at Dave's Market or CornUcopia. Each class will involve brief instructional video clips, hands-on cooking and tasting experiences. Participants will work individually and as part of small groups during instructional sessions. At the end of each class, participants will receive a grocery bundle and a kitchen gadget that serves both as an incentive and implementation support to promote improved cooking frequency and confidence. Participants will be asked to post photos of what they made with their groceries to the GroupMe, and we will encourage them to engage with fellow classmates on the GroupMe to encourage social support of cooking. Participants will earn raffle tickets for each time they post to the GroupMe and attend a class. A raffle drawing for a pressure cooker will be done at the second-assessment meeting (week 12) for the immediate cooking class group and at the last Nourish class for the delayed group (week 20).

The delayed intervention group will commence the Nourish intervention after the post-intervention assessment period is complete (in weeks 13-20).

A research assistant will attend each class to observe time use and lesson objectives covered.

*Second assessment meeting:* Participants will come to a branch of the Cleveland Public Library to complete their post assessment, consisting of PSS, USDA Food Security Screener, and the FLEW, as well as their return food waste log. Additionally, participants will be encouraged to enroll in an optional focus group series to provide feedback on Nourish. The duration of the second-assessment meeting will be approximately 35 minutes, and will occur in Week 12.

*Focus Group Series:* All participants who complete at least 7 of 8 classes of the Nourish intervention will be invited to participate in a series of 2, 90-minute semi-structured, online focus groups to provide additional input on how to improve the lessons. The focus groups timing will depend upon the randomization group. The immediate cooking class group will complete focus groups in weeks 13 and 17; the delayed cooking class group will complete them in weeks 21 and 25. The research team aims to recruit 4-6 participants for each focus group. These sessions will be facilitated by a trained facilitator and additional trained staff will take notes. No participant names will be recorded within the focus group discussion notes. Focus group sessions will be audio-recorded; files will be stored in CWRU Box.

3. There is no more risk than everyday activities. Potential risks will be discussed with eligible individuals during the consent process. Participant risk will be minimized by protecting privacy during weekly class assessments and focus group discussions.

4. Subject data will be collected through the following tools collected before and after the 8-week Nourish curriculum: 2-dietary recalls, Perceived Stress Scale, USDA Food Security Screener, FLEW Assessment, and food waste log, as well as weekly post-class surveys completed online after each of the 8 classes.

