## 17.0 Data Analysis Plan

**Directions: Describe the data analysis plan, including any statistical procedures. If applicable, provide a power analysis, and study/safety endpoints.** Descriptive statistics of Likert scale weekly class survey questions and thematic analyses of weekly survey open-ended questions and focus groups will be used to assess participant perspectives of the pilot study. Classroom observation notes will be used to determine whether the Nourish and intervention is delivered as intended. Feasibility of recruitment and retention will be based on the number of participants recruited and retained through to completion of post-intervention assessments. In addition, we will analyze the pilot data collected. A series of one-way analysis of covariance will be conducted to determine statistically significant differences at post-intervention between the intervention and delayed intervention control groups on each outcome variable, controlling for the pre-treatment assessment scores on the variable analyzed. Outcome variables consist of total volume of food waste, FLEW assessment scores, food security, perceived stress, and diet quality as assessed by the Dietary Inflammatory Index.

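### The baseline waste log is due back at an arm-dependent date, and nothing closes the log and recalls before allocation is disclosed, so two ANCOVA covariates can be recorded with the group known

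*Combined protocol and SAP*

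**What the plan says.** Section 12.0 (Study Design/Procedures) gives the design: "The study follows a randomized controlled trial with a delayed intervention control design". Of the baseline meeting it says: "Regardless of randomized group, all participants will attend this meeting in week 1". Consent is signed there and three surveys are completed: perceived stress, food security and FLEW.

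The rest of baseline comes later: "Two aspects of the baseline evaluation will be conducted after the baseline meeting". These two aspects are a pair of 24-hour dietary recalls by telephone and a log, for which "participants will be asked to weigh and log their food waste for one week". On handing in the log, the section says: "They will be asked to return the log on the first day of class". It gives no separate rule for each arm.

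The class dates do differ by arm: "The immediate cooking class group will receive the Nourish classes in weeks 3-10", whereas "the delayed intervention group will commence the Nourish intervention in weeks 13-20". The second assessment for everyone is in week 12.

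Section 17.0 (Data Analysis Plan) compares the arms after the intervention by ANCOVA, "controlling for the pre-treatment assessment scores on the variable analyzed". Its outcomes are food waste, FLEW scores, food security, perceived stress and diet quality.

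No section says when randomisation takes place, when participants learn their group, or whether the recall interviewers know it.

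**The concern.** ANCOVA in a randomised trial relies on a baseline covariate that allocation cannot have affected. Here two of the covariates are self-reported after the week-1 meeting, and they measure behaviour that the course sets out to change. Someone who knows that a cooking and food-waste course starts next week may weigh, log or recall food differently from someone who knows that the wait is until week 13. Any such difference enters the adjusted comparison as if it were a true baseline difference, and the model then corrects for it.

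The return rule adds a second problem. If the delayed arm may hold its baseline log until its own first class, the two arms work to different deadlines, and one of those deadlines falls after the follow-up assessment.

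**Working it through.** The documents give no power calculation, SD, effect size or expected slope, so there is no stated figure to reproduce. The check has two parts: the calendar, and the algebra of the bias.

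**1. Calendar (Section 12.0)**

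| Event | Immediate arm | Delayed arm |
|---|---|---|
| Consent, three surveys | week 1 | week 1 |
| Two recalls, one-week log | after the meeting | after the meeting |
| First class, when the log is due | week 3 | week 13 |
| Second assessment | week 12 | week 12 |

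- From meeting to log return: 3 − 1 = 2 weeks (immediate) and 13 − 1 = 12 weeks (delayed).
- From second assessment to the delayed arm's log return: 13 − 12 = 1 week. Its baseline log is due after follow-up.
- The immediate arm must know its group by week 3, which is when its log is due.
- Section 26.0 (Research Participant Compensation) pays for baseline measures completed ahead of the classes. That sets no common deadline either, since the delayed arm's classes start in week 13.
- Time available before week 3: 2 weeks, less 1 week of logging, leaves about 1 week.

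**2. Which covariates are exposed**

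Food waste comes from the log and diet quality from the recalls, so both are recorded after the meeting. Stress, food security and FLEW are completed at the meeting and are exposed only if groups are disclosed before or during it.

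**3. Size of the bias**

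The adjusted difference is (difference in follow-up means) − slope × (difference in baseline means). Suppose knowing the group moves the recorded baseline in the immediate arm by δ SD and leaves follow-up unaffected. Then

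bias = −slope × δ.

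Both δ and the slope are assumptions:

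| Shift δ (SD) | slope 0.3 | slope 0.5 | slope 0.7 |
|---|---|---|---|
| 0 | 0 | 0 | 0 |
| 0.2 | −0.06 | −0.10 | −0.14 |
| 0.3 | −0.09 | −0.15 | −0.21 |

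The bias runs opposite to the shift. If the immediate arm logs less waste at baseline because it knows the course is coming, a real reduction is understated. If it logs more, the reduction is overstated. A shift in the delayed arm instead reverses the sign.

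**4. Simulation check**

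The set-up was 20 per arm (Section 5.0), no true effect, two-sided 5% test, t with 37 degrees of freedom and 10,000 runs per cell. The slope equals the baseline-to-follow-up correlation.

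| Slope | Shift | Simulated bias | Type I error |
|---|---|---|---|
| 0.5 | 0 | −0.006 | 0.050 |
| 0.5 | 0.2 | −0.099 | 0.062 |
| 0.5 | 0.5 | −0.251 | 0.138 |
| 0.7 | 0 | 0.004 | 0.052 |
| 0.7 | 0.2 | −0.138 | 0.088 |
| 0.7 | 0.5 | −0.351 | 0.307 |

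The simulated bias agrees with the formula.

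**5. Scale against sampling error**

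The standard error of the adjusted difference is about √[(2/20)(1 − slope²)]. This is √0.075 = 0.27 SD at slope 0.5 and √0.051 = 0.23 SD at slope 0.7. A bias of 0.10 SD is 0.10/0.27 ≈ 0.4 standard errors, and one of 0.21 SD is 0.21/0.23 ≈ 0.9.

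**The case against.** **Assignment before consent.** A reader might infer from the remark about attendance regardless of group that allocation precedes the meeting, and so precedes consent. The documents do not support that. The phrase can equally mean that both future arms share the same first visit. Section 10.0 places consent before the baseline assessments, and no section places assignment earlier. The wording leaves the order open and shows nothing. A claim of group-dependent refusal of consent would rest wholly on that reading, so it is not made here.

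**Contamination as a fact.** A reader might also infer that the log and recalls will be recorded with the group known. The date of return is not the date of recording. A one-week log begun straight after the meeting, and both recalls, could be finished before anyone is told. This objection stands. What remains is that nothing requires that order, while the stated return rule separates the arms by ten weeks.

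**All outcomes affected.** This too goes beyond the text. Unless groups are disclosed by the time of the meeting, only two of the five outcomes are exposed.

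**Size and importance.** The shift and the slope have no source in the documents. At a shift of 0.2 SD and slope 0.5, type I error is 0.06, close to nominal. Section 2.0 sets feasibility, delivery and participant perspectives as the aims, and Section 17.0 presents the between-group tests as additional. These points stand, and they limit severity.

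**Conclusion.** The point holds as a gap in timing that is cheap to close. The log's return rule is arm-dependent as written and, taken literally, puts the delayed arm's baseline log after its follow-up. No other section corrects this or requires baseline collection to close before allocation is known. The integrity of the food waste and diet quality covariates is therefore left to chance.

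The bias range of 0.10 to 0.21 SD is illustrative. It assumes that the shift occurs in one arm only, at baseline only, and with the sizes and slopes given. If knowing the group does not change reporting, there is no bias. Severity is modest, since no efficacy decision rests on these tests. The sequence still matters because the feasibility of the evaluation methods is itself an aim, and Section 3.0 foresees a later test of impact that could inherit it.

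**What to change.** In Section 12.0:

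- Replace return at the first class with one return date in week 2 for all participants, by drop-off or photograph of the log.
- Complete both baseline recalls by the same date.
- State that randomisation and disclosure of the group follow that cutoff, whether or not every log has arrived. Treat baseline data not received by then as missing, so that late returners do not hold up allocation.
- State who holds the allocation until then and whether the recall interviewers know it.

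The about one week left after logging makes this possible without moving any class or assessment. The cost is a few sentences, a way of returning the log in week 2, and shorter notice of the start week. The shorter notice is a real cost, because Section 8.0 expects in-person attendance to be the hardest criterion to meet. Asking participants at consent to hold both class periods would ease it but not remove it.

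### The return rule for the baseline food-waste log, read literally, falls in week 3 for the immediate arm but in week 13 for controls, after the week-12 assessment

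*Combined protocol and SAP*

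**What the plan says.** Section 12.0 (baseline assessment meeting) treats the two arms alike at baseline: "Regardless of randomized group, all participants will attend this meeting in week 1". Everyone is given a kitchen scale and a waste log there. Waste logging and the dietary recalls come later: "Two aspects of the baseline evaluation will be conducted after the baseline meeting". For the log, "participants will be asked to weigh and log their food waste for one week"; the calendar week is not named. The return rule makes no distinction by arm: "They will be asked to return the log on the first day of class". The same paragraph dates the meeting by one arm's calendar only; it "will occur two weeks before the immediate cooking classes" of that group begin.

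For controls, Section 12.0 (weekly classes) says "the delayed intervention group will commence the Nourish intervention in weeks 13-20 (after the second intervention assessment period is complete"). The second assessment meeting is in week 12 for all participants. Its list of tasks includes the stress, food security and FLEW questionnaires "as well as their return food waste log", which in context is the follow-up log.

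Section 17.0 makes total food waste one of five outcomes, each compared between arms by ANCOVA with its own pre-treatment value as covariate. These analyses are introduced as additional to the feasibility and acceptability work.

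**The concern.** The rule ties the return of a baseline measurement to an event that randomisation places at different times. A control who follows it keeps the baseline log for most of the study and hands it in after the follow-up log. Compared with the immediate arm, that leaves more opportunity for the log to be lost, filled in late or from memory, or confused with the follow-up log.

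Two things are at stake. First, the baseline log supplies the covariate for the food-waste ANCOVA, so missing or unreliable baseline values could differ by arm. Section 17.0 states no approach to missing covariates. A control who attends week 12 but never starts class, and is not withdrawn, has no stated point for returning the log. Section 17.0 would still count that person as retained, because retention is judged by completion of the post-intervention assessments. Second, Aim 2 in Section 2.0 asks whether the evaluation methods are feasible. If return rates differed between arms, the pilot could not separate the burden of logging from the difference in due dates.

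**Working it through.** The check is week arithmetic on the schedule in Section 12.0.

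**Inputs.** Baseline meeting and log issue: week 1, both arms. Immediate arm's classes: weeks 3 to 10. Second assessment: week 12. Controls' classes: weeks 13 to 20. Target enrolment (Section 5.0): 20 per arm, 40 in total.

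**Reproducing the plan's own figures.** Meeting to first class, immediate arm: 3 − 1 = 2 weeks, as stated. Length of the class blocks: 10 − 3 + 1 = 8 weeks and 20 − 13 + 1 = 8 weeks, as stated.

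**Applying the return rule to each arm.**

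| | Immediate | Control |
|---|---|---|
| Log issued | week 1 | week 1 |
| Log due (first class) | week 3 | week 13 |
| Issue to return | 3 − 1 = 2 weeks | 13 − 1 = 12 weeks |
| Return relative to week 12 | 3 − 12 = −9 (9 weeks before) | 13 − 12 = +1 (1 week after) |

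The difference in time to return is 12 − 2 = 10 weeks. At target enrolment, 20/40 = 50% of participants would have a baseline log due after the week-12 assessment. These figures are exact only to the calendar week.

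**Does another section give controls an earlier return point?**
- Section 12.0, second assessment meeting: the log listed belongs to the post assessment. Even if controls handed in the baseline log at that visit, it would be 12 − 1 = 11 weeks after issue and alongside the follow-up log. No in-person contact with controls is scheduled between weeks 1 and 12.
- Section 12.0, item 4: data are collected before and after the curriculum, with no date by arm.
- Section 15.0: the logs are listed without dates.
- Section 26.0: the $125 baseline payment covers tasks done before classes start. It rewards completion but sets no return point.
- The baseline recalls, "a series of two 24-hour dietary recalls (via phone calls) lasting approximately 30 minutes each", offer a contact that could be used, but no section says so.

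None supplies one.

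**Room for a common deadline.** The immediate arm has 2 weeks between the meeting and its first class. One week of logging leaves about 2 − 1 = 1 week before week 3.

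**The case against.** The strongest reply is that this is loose drafting and nobody intends controls to keep the log until week 13. The paragraph dates the meeting by the immediate arm's classes. Section 10.0 likewise places consent 2 weeks before the first class, which is true only for that arm. Staff might well collect controls' logs sooner. This is probably right about intent, but the text as written sets the late return and offers controls no alternative.

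A reader might infer that the covariate is measured after the outcome in controls. The documents do not support that. The log is part of the baseline evaluation and follows the week-1 meeting in both arms. A value recorded then is a valid pre-treatment score whenever the log is handed over, so a late return does not by itself undermine the ANCOVA. What remains is narrower: because the logging week is not fixed, the text does not ensure that controls log early.

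A reader might also take the before-and-after wording in Sections 12.0 (item 4) and 26.0 as further evidence of late collection in controls. It is not independent evidence. Applied literally to controls, it would move all their assessments and contradict the week-1 and week-12 meetings. It shares the same loose drafting.

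Finally, the consequence is small. One of five outcomes is touched, the ANCOVAs are secondary to feasibility, and poor log return would itself be informative for Aim 2. This stands, and it limits the weight of the point.

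**Conclusion.** The point holds as a minor defect in a stated rule. Followed as written, the baseline log is due 2 weeks after issue in the immediate arm and 12 weeks after issue in controls, a 10-week difference, and controls' due date falls 1 week after the week-12 assessment. The measurement itself is not scheduled late.

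The conclusion rests on a literal reading of the return sentence and on the absence of any other return point for controls. The documents give no figure for expected loss or late completion, so the effect on the food-waste comparison cannot be computed and no bias is claimed. The correction is still worth making before data collection, because a baseline log that is lost or filled in from memory cannot be recovered afterwards.

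**What to change.** In Section 12.0:
- State that in both arms the baseline log covers the seven days after the baseline meeting.
- Replace the return sentence with a deadline by which the logged weights must reach the team in both arms, no later than the start of week 3. The immediate arm may still hand its log in at its first class.
- Let controls report their weights by a route that needs no extra trip, since Section 25.0 leaves transport costs to participants. One option is a baseline recall call already planned, placed after the logging week.
- Label the log as baseline and keep it separate from the follow-up log. This matters because a control's next scheduled visit is week 12, when the follow-up log is also due.

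The cost is one or two sentences of text. For controls, at least one baseline recall call must fall in the roughly one-week window between the end of logging and week 3, and it will run slightly longer. If only controls report by phone, the reporting mode differs by arm. Using the call in both arms avoids that, at the price of the same scheduling constraint for up to 40 participants.
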